### 5. STUDY TREATMENTS

### 5.1. Description, Storage, Packaging, and Labeling

L606 is an oral inhalation product being developed to accomplish high drug loading efficiency and sustained release properties, enabling a drug therapeutic effect over a prolonged time period and reducing local irritation on the respiratory tract. The L606 inhalation system consists of a mesh-vibrating nebulizer that has been approved in Europe.

L606 inhalation system is an electronic, lightweight, and virtually silent drug delivery device. The vibrating mesh technology generates a fine-particle aerosol. L606 inhalation device includes a main unit, 1 medicup (or a mouthpiece cartridge [MPC]), and/or 1 mouth piece. The device should be stored at room temperature.

The IMP (1.5 mg active pharmaceutical ingredient [API; treprostinil] in 1.0 mL liposome solution and placebo [L606 solution excluding the API]) will be supplied by the Sponsor (or designee), along with the batch/lot numbers and Certificates of Analysis. The IMP will be provided in a type-1 glass ampule and stored according to the instructions on the label.

All IMPs will be stored at the CRU in a location that is locked with restricted access, under conditions according to the instructions on the label.

The dose for administration will be measured in the CRU. Prior to dosing, subjects will be trained to adopt a specific breath pattern to be used during dose administration. Administration instructions and training will be provided and included in separate documents. Subjects will self-administer the dose using the L606 oral inhalation system under the supervision of a trained professional in the CRU.

### 5.2. Study Treatment Administration

Each dose of L606 and placebo solution will be self-administered by the subject via oral inhalation. The entire treatment procedure will be completed within 10 minutes.

Subjects will be administered the IMP in numerical order while seated and may be semi-recumbent but will not be permitted to lie supine for 2 hours after dosing, except as necessitated by the occurrence of an AE(s) and/or study procedures.

The planned emitted dose escalation groups are:

- Cohort 1: 51 µg L606 or placebo volume equivalent to 51 µg
- Cohort 2: 102 μg L606 or placebo volume equivalent to 102 μg
- Cohort 3: 153 µg L606 or placebo volume equivalent to 153 µg
- Cohort 4: 204 µg L606 or placebo volume equivalent to 204 µg
- Cohort 5: 255 µg L606 or placebo volume equivalent to 255 µg
- Cohort 6: 306 µg L606 or placebo volume equivalent to 306 µg
- Cohort 7: 357  $\mu$ g L606 or placebo volume equivalent to 357  $\mu$ g
- Cohort 8: 408 µg L606 or placebo volume equivalent to 408 µg

### 5.3. Randomization

The randomization code will be produced by PPD biostatistics (or a qualified designee) using a computer-generated pseudo-random permutation procedure.

Prior to the start of the study, a copy of the master randomization code will be supplied in sealed envelopes to the PPD CRU pharmacy staff and the biopharmaceutical analyst at the bioanalytical laboratory.

#### 5.4. Blinding

The following controls will be employed to maintain the double-blind status of the study:

- The placebo solution will be identical in appearance to L606.
- The Investigator and other members of staff involved with the study will remain blinded to the treatment randomization code during the assembly procedure.
- Interim bioanalytical data will be provided to PPD in a blinded manner.

To maintain the blind, the Investigator will be provided with a sealed randomization code for each subject, containing details of their treatment. These individual sealed envelopes will be kept in a limited access area that is accessible 24 hours a day. In order to manage subject safety or to support dose escalation decisions (in the event of possibly treatment-related SAEs or severe AEs), the decision to unblind resides solely with the Investigator. If it becomes necessary to break the code during the study, the date, time, and reason will be recorded in the subject's source data and on the individual envelope and will be witnessed by a second person.

### 5.5. Treatment Compliance

The following measures will be employed to ensure treatment compliance:

- All doses will be self-administered under the supervision of a trained professional in the CRU. Administration instructions and training will be provided and included in separate documents.
- At each dose preparation, a predose and postdose inventory will be performed on the dose containers.

## 5.6. Drug Accountability

The Investigator (or designee) will maintain an accurate record of the receipt of the study supplies received. In addition, an accurate drug disposition record will be kept, specifying the amount dispensed to each subject and the date of dispensing. This drug accountability record will be available for inspection at any time. At the completion of the study, the original drug accountability record will be available for review by the Sponsor upon request.

For each batch of unit doses, the empty used unit dose containers will be discarded upon satisfactory completion of the compliance and accountability procedures. Any unused assembled unit doses will be retained until completion of the study.

At the completion of the study, all unused supplies will be returned to the Sponsor or disposed of by the study site, per the Sponsor's written instructions.

## 6. CONCOMITANT THERAPIES AND OTHER RESTRICTIONS

### 6.1. Concomitant Therapies

Subjects will refrain from use of any prescription or nonprescription medications/products (as indicated in the exclusion criteria) during the study until the Follow-up visit, unless the Investigator (or designee) and/or Sponsor have given their prior consent.

Paracetamol/acetaminophen (2 g/day for up to 3 consecutive days); hormone replacement therapy; oral, implantable, transdermal, injectable, or intrauterine contraceptives are acceptable concomitant medications. The administration of any other concomitant medications during the study is prohibited without prior approval of the Investigator (or designee), unless its use is deemed necessary in a medical emergency. Any medication taken by a subject during the course of the study and the reason for its use will be documented in the source data.

### 6.2. Diet

While confined at the study site, subjects will receive a standardized diet at scheduled times that do not conflict with other study-related activities. Subjects will be fasted overnight (at least 8 hours) before collection of blood samples for safety laboratory tests.

On the days with intensive PK assessments (Day 1), meals will be identical for each group.

On Day 1, subjects will be fasted for at least 8 hours prior to dosing until approximately 0.5 to 1 hour after dosing, when a snack will be provided. With the exception of water rinses given as

needed with the dose, subjects will not be allowed fluids from 1 hour prior to until 1 hour after dosing, unless necessary per the Investigator (or designee). Meals will be provided as appropriate at other times. Other than the fluid restrictions on dosing days, water will be freely available at all times.

Foods and beverages containing poppy seeds, grapefruit, or Seville oranges will not be allowed from 7 days prior to Check-in until the Follow-up visit.

Caffeine-containing foods and beverages will not be allowed from 48 hours before Check-in until the Follow-up visit.

Carbonated drinks (including sparkling water and soda) will not be allowed from 48 hours before Check-in until Discharge from the CRU.

Consumption of alcohol will not be permitted from 72 hours prior to Check-in until Discharge from the CRU.

### 6.3. Smoking

Subjects will not be permitted to use tobacco- or nicotine-containing products within 6 months prior to Check-in until the Follow-up visit.

#### 6.4. Exercise

Subjects are required to refrain from strenuous exercise from 7 days prior to Check-in until the Follow-up visit and will otherwise maintain their normal level of physical activity during this time (ie, will not begin a new exercise program or participate in any unusually strenuous physical exertion).

#### 6.5. Blood Donation

Subjects are required to refrain from donation of blood within 6 weeks prior to Screening, plasma within 6 weeks prior to Screening, and platelets within 6 weeks prior to Screening until 56 days after the Follow-up visit.

#### 6.6. Contraception

Female subjects who are of nonchildbearing potential will not be required to use contraception. Females of nonchildbearing potential are defined as permanently sterile (ie, due to hysterectomy or bilateral oophorectomy) confirmed by history, or postmenopausal (defined as at least 12 months postcessation of menses without an alternative medical cause). Postmenopausal status will be confirmed with a screening serum follicle-stimulating hormone level >40 mIU/mL.

Female subjects of childbearing potential must be willing to use a highly effective method of birth control (ie, contraceptive measure with a failure rate of <1% per year if used properly) in conjunction with a barrier contraception (ie, male or female condom with spermicide) from the

time of signing the ICF until 90 days after the dose of study drug. Highly effective methods of contraception include:

- intrauterine device (IUD; eg, Mirena®). Steel or copper IUDs are not acceptable
- established use of oral, implantable, transdermal, or injectable hormonal method of contraception associated with inhibition of ovulation
- ensure male partner is sterilized (performed at least 90 days prior to the Screening visit), with verbal confirmation of surgical success (for female subjects on the study, the vasectomized male partner should be the sole partner for that subject)
- bilateral tubal ligation or occlusion (performed at least 90 days prior to the Screening visit)
- bilateral salpingectomy.

Male subjects will be surgically sterile for at least 90 days or, when sexually active with female partners of childbearing potential, will be required to use a male condom with spermicide from Check-in until 90 days after the dose of study drug. Sexual intercourse with female partners who are pregnant or breastfeeding should be avoided unless condoms are used from the time of the first dose until 90 days after the dose of study drug. Male subjects are required to refrain from donation of sperm from Check-in until 90 days after the dose of study drug.

Subjects who practice true abstinence, because of the subject's lifestyle choice (ie, the subject should not become abstinent just for the purpose of study participation), are exempt from contraceptive requirements. Periodic abstinence (eg, calendar, ovulation, symptothermal, postovulation methods) and withdrawal are not acceptable methods of contraception. Subjects who practice true abstinence as a lifestyle choice agree to remain abstinent for 90 days after the last dose of study drug.

For subjects who are exclusively in same-sex relationships, contraceptive requirements do not apply. However, subjects who are exclusively in same-sex relationships agree to refrain from heterosexual contact for 90 days from the last dose.

## 7. STUDY ASSESSMENTS AND PROCEDURES

Every effort will be made to schedule and perform the procedures as closely as possible to the nominal time, giving considerations to appropriate posture conditions, practical restrictions, and the other procedures to be performed at the same timepoint.

When multiple assessments (ie, ECGs, vital signs, and blood draws for PK or clinical laboratories) are scheduled to be performed at the same timepoint, the blood draws will be obtained at the scheduled timepoint, and ECGs and vital signs will be performed prior to the scheduled timepoint. The order of events should always be 1) resting for ECG, 2) vital signs, 3) blood collection, and 4) other assessments.

### 7.1. Pharmacokinetic Assessments

## 7.1.1. Sample Collection and Processing

Blood samples (approximately  $1 \times 4$  mL) will be collected by venipuncture or cannulation at the times indicated in the Schedule of Assessments in Appendix 5. Furthermore, up to 3 additional blood samples may be taken from each subject per treatment period, with the maximum volume of blood withdrawn per subject not exceeding the limit detailed in Appendix 3. Any changes to the scheduled times of PK assessments will be agreed with the Sponsor and documented in the TMF. Samples taken from subjects who received placebo will not be analyzed.

Procedures for collection, processing, and shipping of PK blood samples will be detailed in a separate document.

## 7.1.2. Analytical Methodology

Plasma concentrations of treprostinil will be determined using a validated liquid chromatography by tandem mass spectrometric analysis method. Specifics of the analytical method will be provided in separate documents.

### 7.2. Safety and Tolerability Assessments

#### 7.2.1. Adverse Events

Adverse event definitions, assignment of severity and causality, and procedures for reporting SAEs are detailed in Appendix 1.

Between the time of signing the ICF and drug administration, only SAEs will be recorded. All AEs (serious and nonserious) will be recorded as of the time of dose administration until final discharge from the study. Subjects will be observed for any signs or symptoms and asked about their condition by open questioning, such as "How have you been feeling since you were last asked?", at least once each day while resident at the study site and at each study visit. Subjects will also be encouraged to spontaneously report AEs occurring at any other time during the study.

All nonserious AEs, whether reported by the subject voluntarily or upon questioning, or noted on physical examination, will be recorded from initiation of study drug until study completion. Nonserious AE information should also be collected from the start of a washout period or other observational period intended to establish a baseline status for the subjects. Serious AEs will be recorded from the time the subject signs the ICF until study completion. The nature, time of onset, duration, and severity will be documented, together with an Investigator's (or designee's) opinion of the relationship to study drug.

Adverse events recorded during the course of the study will be followed up, where possible, until resolution. This will be completed at the Investigator's (or designee's) discretion.

## 7.2.2. Clinical Laboratory Evaluations

Blood and urine samples will be collected for clinical laboratory evaluations (including clinical chemistry, hematology, urinalysis, serology, and coagulation assessments) at the times indicated in the Schedule of Assessments in Appendix 5. Clinical laboratory evaluations are listed in Appendix 2. Additional clinical laboratory evaluations will be performed at other times if judged to be clinically appropriate or if the ongoing review of the data suggests a more detailed assessment of clinical laboratory safety evaluations is required.

Subjects will be asked to provide urine samples for drugs of abuse screen and cotinine test, and will undergo an alcohol breath or urine test at the times indicated in the Schedule of Assessments in Appendix 5. For all female subjects, a pregnancy test will be performed at the times indicated in the Schedule of Assessments in Appendix 5.

An Investigator (or designee) will perform a clinical assessment of all clinical laboratory data.

### 7.2.3. Vital Signs

Supine blood pressure, supine pulse rate, respiratory rate, and oral body temperature will be assessed at the times indicated in the Schedule of Assessments in Appendix 5. Vital signs may also be performed at other times if judged to be clinically appropriate or if the ongoing review of the data suggests a more detailed assessment of vital signs is required.

Day 1 predose blood pressure, pulse rate, and respiratory rate will be measured in triplicate at approximately 2-minute intervals. The median value will be used as the baseline value in the data analysis. All subsequent measurements will be performed singly. Oral body temperature will be measured singly.

Subjects must be supine for at least 5 minutes before blood pressure and pulse rate measurements.

For orthostatic vital sign measurements, the supine blood pressure and pulse rate will be measured after the subject has been supine for at least 5 minutes. The subject will then stand for at least 2 minutes and the standing blood pressure and pulse rate will be measured.

### 7.2.4. 12-Lead Electrocardiogram

Resting 12-lead ECGs will be recorded after the subject has been supine and at rest for at least 5 minutes at the times indicated in the Schedule of Assessments in Appendix 5. Single 12-lead ECGs will be repeated twice and the results averaged if either of the following criteria apply:

- QT interval corrected for heart rate using Fridericia's method (QTcF) value >500 msec
- QTcF change from the baseline (predose) is >60 msec.

Additional 12-lead ECGs may be performed at other times if judged to be clinically appropriate or if the ongoing review of the data suggests a more detailed assessment of ECGs is required. The Investigator (or designee) will perform a clinical assessment of each 12-lead ECG.

## 7.2.5. Continuous 12-Lead Holter Monitoring

Electrocardiogram parameters will be measured using a 24-hour continuous 12-lead Holter monitor beginning the night of Day -1 in order to obtain 8 to 12 hours of predose baseline data, and through 24 hours postdose.

Subjects will be connected to a Holter ECG recording device and the ECG recording will be started. Subjects will be instructed to avoid strenuous physical exercise or any other activity that could interfere with the quality of the Holter ECG recording or lead to detachment of ECG skin electrodes during the continuous Holter recording period.

During the Holter recording period, the Holter leads should be checked prior to each scheduled PK blood collection. Subjects should be instructed to inform appropriate study site personnel immediately upon discovery of a device or lead failure. Any failures of the Holter device or accessory hardware (electrodes, leads, batteries, etc.) will be recorded in the source documents.

All data will be sent for central ECG evaluation. A data file containing central ECG evaluation will be provided for inclusion in study analysis. Any Holter ECG reports provided to the site will be archived as source documentation only. Holter ECG start and end times should be recorded on the CRF.

Details of the Holter ECG recording will be provided in the ECG manual provided by the central reader.

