Appendix 5: Schedule of Assessments

# Table 3:Schedule of Assessments

	Screening (Day -28 to Day -2)		Treatment Period			Follow-up Visit
		Check-in (Day -1)	Day 1	Day 2	Discharge (Day 3)	Day 8 to Day 11 (7 to 10 days postdose)
Informed consent	Х					
Demographic data	Х					
Inclusion/exclusion criteria	Х	Х				
Medical history	Х	$X^{a}$				Х
Serology	Х					
Urine drugs of abuse screen (including cotinine)	х	Х				
Alcohol breath or urine test	Х	Х				
Pregnancy test	Х	Х				Х
Study residency						
Check-in		Х				
Discharge					Х	
Nonresidential visit	Х					Х
Dosing with L606 or placebo			Х			
Inhalation administration training b		Х				
Safety and tolerability						
Adverse events c	Х	Х	Х	Х	Х	Х
Concomitant medication	Х	Х	Х	Х	Х	Х
Physical examination d	Х	Х			Х	Х
Body weight, height, and BMI e	Х	Х				
Safety 12-lead ECG f	Х	Х	Х	Х	Х	Х
12-Lead Holter monitor recording g		Х	Х	Х		
Vital signs h	Х	Х	Х	Х	X	Х
Oxygen saturation i		Х		Х	Х	Х
Spirometry j	Х	Х		Х	Х	Х
Clinical laboratory evaluations k	Х	Х		Х	Х	Х
PT, aPTT, INR	Х					
Methemoglobin 	X			Х		
Pharmacokinetics						
Blood sampling for PK analysis of treprostinil m			Х	Х		

Protocol

Abbreviations: AE = adverse event; aPTT = activated partial thromboplastin time; BMI = body mass index; ECG = electrocardiogram; ICF = Informed Consent Form; INR = international normalized ratio; PK = pharmacokinetic; PT = prothrombin time; SAE = serious adverse event.

- a Updated medical history (from Screening).
- b All doses will be self-administered under the supervision of a trained professional in the CRU. Administration instructions and training will be provided and included in separate documents.
- c Between the time of signing the ICF and drug administration, only SAEs will be recorded. All AEs (serious and nonserious) will be recorded as of the time of dose administration until final discharge from the study.
- d Full physical examination at Screening and symptom-directed physical examinations at Check-in, Discharge, and Follow-up.
- e Weight is measured at Screening and Check-in. Height and BMI is measured only at Screening.

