- f Twelve-lead safety ECGs will be collected at Screening; Check-in; Day 1 predose, 4, and 24 hours postdose; Discharge; and Follow-up. Subjects will be required to rest in a supine position for at least 5 minutes prior to the ECG extraction timepoints. Assessment times postdose are relative to the end of the inhalation treatment.
- g Electrocardiogram parameters will be measured using a 24-hour continuous 12-lead Holter monitor beginning the night of Day -1 in order to obtain 8 to 12 hours of predose baseline data, and through 24 hours postdose.
- h Supine blood pressure, supine pulse rate, and respiratory rate will be taken at Screening; Check-in; Day 1 predose and at 0.25, 30, 1, 1.5, 2, 4, 8, 12, and 24 hours postdose; Discharge; and Follow-up. Oral body temperature will be taken at Screening; Check-in; Day 1 predose; Discharge; and Follow-up. Orthostatic vital signs will be assessed at Check-in; Day 1 predose; and at 1, 4, and 8 hours postdose. Assessment times postdose are relative to the end of the inhalation treatment.
- i Oxygen saturation will be measured at rest by standard pulse oximetry Check-in, Day 2, and Discharge.
- j Spirometry (forced expiratory volume in 1 second and forced vital capacity) will be measured in a sitting position, if possible, at Screening, Check-in, Day 2, Discharge, and Follow-up. Pre- and post-bronchodilator spirometry testing will be completed at Screening using albuterol; all other timepoints will not require post-bronchodilator testing.
- k Clinical laboratory evaluations including clinical chemistry, hematology, and urinalysis.
-  Methemoglobin will be measured noninvasively using a finger probe.
- m Blood sampling for PK analysis of treprostinil at Day 1 predose and at 0.25, 0.5, 1, 1.5, 2, 4, 6, 8, 10, 12, 14, 16, and 24 hours postdose. Sampling times postdose are relative to the end of the inhalation treatment.

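### The Holter is labelled a 24-hour recording, but the start and end given in the same sentence span 32 to 36 hours

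*Protocol*

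**What the plan says.** Protocol Section 7.2.5 describes the Holter in one sentence. It gives a nominal length, a start and a purpose: "24-hour continuous 12-lead Holter monitor beginning the night of Day -1 in order to obtain 8 to 12 hours of predose baseline data". It then gives the end: "and through 24 hours postdose". Footnote g of Table 3 (Appendix 5) has the same sentence, including "beginning the night of Day -1 in order to obtain 8 to 12 hours of predose baseline data, and through 24 hours postdose", so the schedule does not settle the matter.

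Three other provisions bear on the length:

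- The Table 3 row "12-Lead Holter monitor recording" is marked at Check-in (Day -1), Day 1 and Day 2.
- Section 7.2.5 wants the leads checked before each scheduled PK draw while the Holter is running. Footnote m lists draws up to 24 hours postdose, including 14, 16 and 24 hours.
- Section 7.2.5 leaves the practical detail to another document: "Details of the Holter ECG recording will be provided in the ECG manual provided by the central reader". It also has the actual start and end times entered on the CRF.

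**The concern.** A recording that begins 8 to 12 hours before dosing and lasts 24 hours cannot reach 24 hours after dosing. Whoever programmes the recorder or writes the ECG manual has two incompatible instructions in one sentence, a duration and an end point, and could follow either.

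This is the first-in-human study of L606. Section 2.2.1 lists 12-lead ECG parameters among the primary safety endpoints, and Section 7.2.5 says the centrally read Holter file will go into the study analysis. Within the 24 hours after dosing, footnote f schedules safety ECGs only at 4 and 24 hours. If the shorter figure were followed, the later part of the postdose period would have no scheduled ECG recording, and hours that were not recorded cannot be recovered afterwards.

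**Working it through.** **Inputs** (Section 7.2.5 and Table 3 footnote g): nominal length 24 h; predose segment p = 8 to 12 h; recording to end 24 h postdose. The inhalation itself, at most 10 minutes (Section 5.2), is ignored; it would lengthen the required window slightly.

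**Step 1. Can the stated 24 h be reproduced from the stated start and end?**
Required length = p + 24.
- p = 8: 8 + 24 = 32 h
- p = 12: 12 + 24 = 36 h

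It cannot. The label falls short by 32 − 24 = 8 h to 36 − 24 = 12 h.

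**Step 2. What would a recording of exactly 24 h cover?**
Postdose hours covered = 24 − p; postdose hours missed = 24 − (24 − p) = p.

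| Predose hours | Length needed | Postdose hours covered by a 24 h recording | Postdose hours missed | Share of the 24 h postdose window |
|---|---|---|---|---|
| 8 | 32 | 16 | 8 | 8/24 = 33% |
| 10 | 34 | 14 | 10 | 10/24 = 42% |
| 12 | 36 | 12 | 12 | 12/24 = 50% |

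**Step 3. Which of the two readings agrees with the rest of the protocol?**
- *Table 3.* Twenty-four hours from a start on the evening of Day -1 ends on the evening of Day 1, which leaves nothing to record on Day 2. As an illustration, with an assumed 08:00 dose (the protocol gives no dosing time) and 10 to 12 h predose, a 24 h recording would run from 20:00–22:00 on Day -1 to 20:00–22:00 on Day 1. With the same dose time and 8 h predose, it would end at midnight. Recording through 24 h postdose ends on Day 2, as marked.
- *Lead checks.* With p = 12, a 24 h recording stops before the 14, 16 and 24 h PK draws; with p = 8, before the 24 h draw. Recording through 24 h postdose covers all of them.

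Both checks favour the explicit end point over the label.

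**Step 4. If the explicit end point governs**, the recording lasts 32 to 36 h and no postdose hours are lost.

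**The case against.** The strongest reply is that nothing is lost under the protocol as it stands. It fixes the start and the end of recording, and does so twice; Table 3 agrees with that end. Only the label disagrees, and it might be meant as the type of monitor or the length of the postdose segment. Details are left to an ECG manual that is not available here, and CRF start and end times would reveal a short recording.

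Most of this stands. A reader might infer that the plan as written discards the last third to half of the postdose window. The documents do not support that, because the same sentence requires recording through 24 hours postdose. The loss is conditional on someone following the 24-hour figure.

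The reply does not remove the inconsistency. In the sentence, the 24-hour recording is the one that begins on the night of Day -1, so the label does not naturally describe the postdose segment alone. If it describes the device's capacity, the protocol does not say how such a device would record 32 to 36 hours continuously. The manual has to implement the protocol and inherits the conflict, and CRF times document a shortfall without preventing it.

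Two further inferences should also be resisted:

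- A reader might argue that a 24-hour recording leaves no postdose hour at the same clock time as the baseline, which would spoil a time-matched comparison. The protocol defines no such Holter analysis and leaves further statistical detail to the SAP, so this is no error in the document.
- A reader might call the Holter the only ECG information between the safety tracings. That is true only of scheduled recordings, since Section 7.2.4 allows additional 12-lead ECGs.

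It is also fair to note that no stopping criterion in Section 3.7 uses ECG or Holter data and that Section 8.4 plans no formal safety testing.

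**Conclusion.** The point holds as an error in the stated recording length. Section 7.2.5 and Table 3 footnote g give 24 hours for a window that their own start and end make 32 to 36 hours, a discrepancy of 8 to 12 hours in an operative procedure. This part rests on the protocol's figures alone.

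The consequence is conditional. Only if the recorder or the ECG manual is set to 24 hours would recording stop 12 to 16 hours postdose. In that case 8 to 12 of the 24 postdose hours (33% to 50%) would go unrecorded, and no ECG would be scheduled from then until 24 hours postdose. This assumes that the full 8 to 12 hours of predose baseline is obtained first. If the stated end point is followed, the loss is zero.

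The correction is worth making before the first subject is dosed, because it costs little and missing ECG hours cannot be replaced.

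**What to change.** In Section 7.2.5 and in footnote g of Table 3, remove the 24-hour label. Describe a single continuous 12-lead Holter recording that starts on the night of Day -1, 8 to 12 hours before dosing, and runs through 24 hours postdose, with the total stated as about 32 to 36 hours. Put the same duration in the central reader's ECG manual, and confirm that the recorder's capacity covers it.

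The cost is a wording change in two places and a check of the manual and the device. No visit is added: Table 3 already marks the Holter on Day -1, Day 1 and Day 2, and subjects stay in the unit until Day 3 (Section 3.1).
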